## 4.6.5 Patient Reported Outcomes (PROs)

Baseline data for PROs will be collected pre-dose on Day 1 (Randomization Visit 3) and summarized and listed to include:

- Proportion of subjects with baseline mMRC  $\geq 2$  (n, %)
- Baseline SGRQ component scores and total score
- BDI component scores and focal score

#### 4.7 Medical History

The medical history events except for COPD history will be coded by System Organ Class (SOC) and Preferred Term (PT) using the Medical Dictionary for Regulatory Activities (MedDRA). The MedDRA version used for reporting the study will be described in the relevant table and listing footnotes. The number and percentage of subjects in each SOC and PT will be summarized based on FAS by treatment group and overall.

Each subject's medical history will be listed by SOC and PT for the Randomized Set.

#### 4.8 **Prior and Concomitant Medication**

Data on prior and concomitant medication will be summarized based on the Safety Set by treatment group and overall.

Any medication taken prior to the first dose of double-blind study treatment will be documented as prior medication. Any medication taken after the first dose of study drug will be documented as a concomitant medication.

For partial/missing start/end date of the medication, the imputation rule below will be applied before the summary:

- Start date:
  - If Year and Month exists but Day is missing, impute the Day as 1;
  - If Year exists but Month and Day are missing, impute the Month and Day as January 1st;
  - If Year is missing or the entire date is missing, do not impute but assume the medication started after the first dose and to be considered as a concomitant medication.
- End date:
  - If Year and Month exists but Day is missing, impute the Day as the last day of the month;
  - If Year exists but Month and Day are missing, impute the Month and Day as December 31st;
  - If Year is missing or the entire date is missing, and the status is not ongoing, do not impute but assume the medication ended after the first dose and to be considered as a concomitant medication.

Both prior and concomitant medications will be coded using the World Health Organization Drug Dictionary (WHODRUG). The WHODRUG version used for reporting the study will be described in the relevant table and listing footnotes.

The Anatomical Therapeutic Chemical (ATC) level 1 term and PTs for prior medications will be summarized by treatment group and overall. Concomitant Medications for COPD (e.g.

concomitant bronchodilators, concomitant corticosteroids) will be identified and summarized in a similar manner in separate tables.

Each subject's prior and concomitant mediation will be listed by ATC level 1 and PT for the Randomized Set.

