## 5.7 Concomitant Medications

All concomitant medications taken during the study (from signing informed consent to post-study follow-up) must be recorded with indication, daily dose, and start and stop dates of administration in the CRF. All subjects will be questioned about concomitant medication at each clinic visit and at follow up.

Medications taken within 28 days prior to screening and prior to dosing with study medication will be documented as a prior medication. Medications taken after dosing with study medication will be documented as concomitant medications.

Subjects will abstain from all prohibited medications as described in the exclusion criteria section of this protocol (Section 4.2.2). Use of prohibited medication during the study will be deemed a protocol deviation and such subjects will be assessed by Mylan or designee regarding potential need to early terminate study drug (e.g., for safety reasons – see Section 4.2.4).

Prior to the ipratropium reversibility testing during screening, short acting bronchodilators must be withheld for  $\geq 6$  hours.

Inhaled maintenance corticosteroid therapy will be continued at the allowed maintenance dose throughout the treatment and washout periods. Salbutamol will be allowed as required (or “PRN”) during the study. Salbutamol must be withheld for  $\geq 6$  hours before the first spirometry performed at each study visit and during the course of the entire visit when serial spirometry is performed.

Use of salbutamol as a rescue medication (number of daily puffs) will be documented in the daily diary and recorded in the eCRF. If a subject has used rescue medication on the same day as the clinic visit, prior to spirometry assessments, then both the number of puffs and the time of administration will be documented to allow evaluation of impact, if any, on spirometry measurements.

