#### 4.4.2 **Protocol Deviations**

Major analysis protocol deviations that could potentially affect the efficacy conclusions of the study will be identified prior to database lock. Major analysis protocol deviations may include, but are not limited to:

- Randomized subjects who did not satisfy inclusion criteria
- Randomized subjects who did not satisfy exclusion criteria
- Subjects whose randomized and actual treatments differ at any time point
- Subjects who received an excluded concomitant treatment or medication
- Subjects who are not 80-120% compliant with study medication
- Subjects who received rescue medication within 6 hours prior to spirometry testing

Subjects with major analysis protocol deviations will be identified before the database lock and provided in a listing of subjects excluded from per-protocol (PP) efficacy analyses. In addition, a listing of all major deviations will be provided whether they impact the analysis or not. All decisions to exclude subjects from the PP analysis set will be made prior to unblinding in the final blinded data review (BDR) meeting and report.

The PD summaries will include the following information, using Randomized Set:

- the number and percentage of subjects with a major PD by treatment group and overall and by type of deviation
- the number and percentage of subjects with a major PD leading to exclusion from the PP by treatment group and overall, and by type of major deviation leading to exclusion
- the number and percentage of subjects with a major PD related to COVID-19 by treatment group and by type of deviation

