## 4.11.2 Adverse Events

All AEs that occur after the first dose of double-blind study medication to 30 days after the last dose of study medication will be considered to be treatment-emergent adverse events (TEAEs).

Where dates are missing or partially missing, adverse events will be assumed to be treatmentemergent, unless there is clear evidence (through comparison of partial dates) to suggest that the adverse event started prior to the first dose of study medication or more than 30 days after the last dose of study medication.

The MedDRA will be used to code the primary SOC and the PT of the AEs. The MedDRA version used for reporting the study will be described in relevant table and listing footnotes.

There are three categories of AE severity: Mild, Moderate and Severe. For adverse events with missing intensity, they are counted in the most conservative way as Severe in the summary by intensity.

There are five categories of AE Relationship to study treatment: Definite, Probable, Possible, Unlikely, Unrelated/Not Related. An adverse event is considered related to the study treatment if the relationship to the study treatment is considered "Definite", "Probably Related", "Probable" or 'Possible'.

All AEs and all TEAEs will be listed by subject.

All AE tables will be restricted to treatment-emergent AEs unless otherwise specified. Each subject will be counted only once within each PT or SOC. If a subject experiences more than one AE within a PT or SOC, only the AE with the strongest relationship or the worst severity, as appropriate, will be included in the summaries of relationship and severity. AEs with missing classifications regarding relationship to study treatment will be considered as related to study drug.

TEAEs will be sorted in descending order of frequency (total column) by SOC and by PT within each SOC, unless otherwise stated, alphabetical order will be used for same frequency of SOC or PT.

An overall summary of TEAEs for both the subjects with at least one AE and the total number of AEs in following categories are planned to be displayed: any TEAE, any serious TEAE, TEAE by relationship (related, not related), TEAE by severity, TEAE leading to treatment discontinuation, and any TEAEs related to a public health emergency.

The following summaries of the total number of TEAEs and the number and percentage of subjects with at least one TEAE will be provided. These will also be presented by primary SOC and PT for each treatment group:

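### SAP 4.8 treats a drug with an unknown start year as started on study even when its recorded stop date is before the first dose, so a washed-out LAMA can appear in the concomitant COPD medication table (minor)

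*SAP*

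**What the plan says.** SAP Section 4.8 gives two definitions. "Any medication taken prior to the first dose of double-blind study treatment will be documented as prior medication", and "Any medication taken after the first dose of study drug will be documented as a concomitant medication". Protocol Section 5.7 agrees on the second: "Medications taken after dosing with study medication will be documented as concomitant medications".

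SAP 4.8 then handles incomplete dates: "For partial/missing start/end date of the medication, the imputation rule below will be applied before the summary". A start date with a known year is filled in to the first day of the month or to 1 January. If the year or the whole date is missing, the instruction is to "do not impute but assume the medication started after the first dose and to be considered as a concomitant medication". The end-date bullets act only on incomplete end dates. None of them says what a complete end date before the first dose does to the start-date assumption.

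The affected output is named in the same section. Beside the prior-medication summary, COPD drugs ("concomitant bronchodilators, concomitant corticosteroids) will be identified and summarized in a similar manner in separate tables") get their own concomitant tables, by treatment group and overall on the Safety Set.

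**The concern.** Assuming concomitant use is a sensible conservative default when nothing shows that the drug ended before dosing. It is wrong when the stop date is recorded and lies before the first dose, because the record is then given a start later than its end.

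This design produces records of that kind. Protocol Table 5-1 requires LAMA users to stop before the reversibility test, and moves users of LAMA/LABA and triple combinations to the product without the LAMA. Protocol Sections 5.7 and 6.1.1 collect drugs taken in the 28 days before consent and everything taken from consent onward, so stopped LAMAs will be in the database. If the start year of one is unknown, the concomitant bronchodilator table would show a drug of the test product's own class as used on treatment when it was not.

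A second, smaller effect concerns stable background LABA or ICS. It is correctly concomitant while ongoing. But if it is assumed to have started after the first dose, it was by assumption not taken before it, and it falls out of the prior-medication table.

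**Working it through.** The plan states no figure on this point, so the check applies the rule as written to the possible records and compares the result with the section's own definitions.

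**Where the washed-out LAMA's stop date falls.** Inputs: washout of 7 days before the reversibility test (Protocol Table 5-1); reversibility test at Visit 2, which is 4 to 10 days before Visit 3 (Protocol Section 6.1.1); first dose at Visit 3.

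- Stop before first dose, at least: 7 + 4 = 11 days to 7 + 10 = 17 days.
- Footnote 1 of SAP Table 1 gives 14 days for LAMAs where the protocol gives 7. The two need to be reconciled. With 14 days the result is 14 + 4 = 18 to 14 + 10 = 24 days.

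On either figure, a subject who followed the washout has a stop date clearly before the first dose.

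**What the rule does with each record.**

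| Start date | Stop date | SAP 4.8 rule, literally | SAP 4.8 definitions |
|---|---|---|---|
| Known, before first dose | Known, before first dose | Prior | Prior |
| Year missing | Known, before first dose | Concomitant, assumed to start after first dose | Prior |
| Year missing | On or after first dose, or ongoing | Concomitant only | Concomitant, and also prior unless it began on study |

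The first two rows can be the same LAMA with the same stop date. They differ only in whether the patient remembered the start year, yet they go to different tables. In the second row the assumed start is at least 11 days after the recorded stop, which is impossible.

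**Comparison within the SAP.** The adverse-event date rule in SAP Section 4.11.2 uses the same conservative default but has an escape: events with missing dates are treatment-emergent "unless there is clear evidence (through comparison of partial dates) to suggest that the adverse event started prior to the first dose". The medication rule has no such clause.

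**Effect of the correction.** If the stop date is checked first, the second row becomes prior only. A record with a missing start date that is ongoing stays concomitant, so the conservative default is kept where it is needed.

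**The case against.** The strongest reply is that the trigger is narrow and the reach is short. Protocol Section 5.7 requires start and stop dates to be recorded, and SAP Section 4.10.1.3 says missing data will be queried. A start date with only the year known becomes 1 January of that year, which is correctly pre-study for a long-standing drug. Only a start year still missing after query, combined with a stop date before dosing, gives a false concomitant entry. SAP 4.8 also plans a by-subject listing where a recorded stop date could be checked, although its columns are not specified. All of this stands and limits the point, but it does not make the rule right for the records it catches.

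Three stronger readings are tempting, and the documents do not support them.

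- *A reader might infer that subjects would be removed from the per-protocol set.* SAP Section 4.4.2 does list "Subjects who received an excluded concomitant treatment or medication" among possible major deviations. But the date rule is stated to apply before the summaries, per-protocol exclusions are decided at the blinded data review, and Protocol Section 5.7 has the sponsor or its designee assess prohibited use. No text says that the derived flag drives those decisions. An effect is possible but not shown.
- *A reader might infer that the drug would be reported as prohibited on-study use.* No prohibited-medication table is planned. The rule assigns only the label concomitant; the rest is inference from Protocol Table 5-1.
- *A reader might want a count.* Assuming that 20–40% of 320 subjects took a LAMA before screening and that 5–20% of those start years stay unknown gives 320 × 0.20 × 0.05 = 3.2 to 320 × 0.40 × 0.20 = 25.6 subjects. Neither share is in the documents. Putting in the only treatment rate they quote, 7.9% with regular COPD treatment in a Chinese survey, gives 320 × 0.079 × (0.05 to 0.20) = 1.3 to 5.1. That survey is not the trial population and does not concern LAMAs. The spread shows that no figure can be relied on.

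**Conclusion.** The rule is wrong as written, and the point is minor. For a medication with a missing start year and a recorded stop before the first dose, it gives an impossible order of dates and a class that contradicts both the SAP and protocol definitions. The consequence is misplaced entries in descriptive medication tables: a false entry under concomitant COPD medication for a washed-out LAMA and, read literally, a lost entry under prior medication for ongoing background LABA or ICS.

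The efficacy results are not at risk. The baseline LABA and ICS variables are taken as collected (SAP Section 4.6.4), FAS strata are those assigned at randomization (SAP Section 4.5), and no efficacy model uses the derived prior or concomitant class. The conclusion rests on the literal text of SAP 4.8 and on at least one such record remaining after data queries; how many there will be is unknown.

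**What to change.** Replace the start-date bullet for a missing year or wholly missing date with a rule that looks at the stop date, after any imputation of that date:

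- Stop date before the first dose: prior only.
- Stop date on or after the first dose, or drug ongoing: both prior and concomitant, unless the CRF shows that it started on study, in which case concomitant only.
- Stop date missing and drug not ongoing: concomitant, as the current text has it.

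This brings the medication rule into line with the adverse-event rule in SAP Section 4.11.2 and keeps the conservative default wherever the stop date does not settle the matter. The cost is one SAP sentence and one derivation line, with no new data and no change to any efficacy analysis.

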## 4.9 Treatment Compliance

Subjects will take nebulized study drug (3mL sealed plastic vial) once daily during the 12-week double-blind placebo-controlled treatment period.

The number of dispensed, used, unused and lost vials will be counted and recorded as part of the drug accountability. The primary assessment of compliance will be based on the vial counts.

Compliance is based on the count of number of study drug vials taken as recorded on the Drug Accountability eCRF page. Treatment compliance in percent will be calculated as:

Compliance (%) = (Number of vials taken / Number of expected vials)  $\times$  100

where Number of expected vials =  $1 \times \text{study drug exposure}$ 

Details of study drug exposure are described in Section 4.11.1.

The compliance will be classified (e.g. <80%, 80%-120\%, >120%). If the compliance is outside of 80%-120%, a subject is considered non-compliant. The number and percentage of subjects in the above categories will be summarized based on Safety Set by treatment group and overall.

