### 5.1.2 Study Medication Compliance

Study medication compliance will be assessed during the study on the basis of:

1. Number of used and unused vials at each visit.
2. Subject diary entries.

The primary assessment of compliance will be a count of the used and unused vials; however, in the event of missing vials, the subject diary entries will be utilized to assess and record study medication compliance. The number of used and unused vials and/or diary card data on compliance will be recorded in the CRF.

Study medication compliance will be checked at Visits 4-6 to ensure that subjects are compliant (i.e., who are considered to have received 80% - 120% of the total number of doses that should have been administered in between study visits). Subjects who are non-compliant will be re-trained on the requirements of the study.

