**Table 5-1: Restricted Medications**

Medication	Washout Required (or Modification) and Prohibited Time Period
Any ICS at a dose of >1000 mcg/day fluticasone propionate or equivalent.	Subjects on a dose >1000 mcg/day fluticasone propionate or equivalent should have their dose modified to be on a stable dose of $\leq$ 1000 mcg fluticasone propionate or equivalent for at least 30 days prior to the Ipratropium Reversibility test at screening and continued through to end of V6.
LAMA – e.g., tiotropium, glycopyrronium bromide, aclidinium, umeclidinium. PDE4 inhibitors – roflumilast.	7 days prior to the Ipratropium Reversibility test at screening and prohibited during the course of the study through to end of V6.
LABA – e.g., salmeterol, formoterol fumarate, arformoterol tartrate, indacaterol, vilanterol, olodaterol. ICS/LABA products, e.g., salmeterol/fluticasone propionate, vilanterol/fluticasone furoate, formoterol/budesonide. LAMA/LABA combination products, e.g., umeclidinium/vilanterol. LAMA/ICS/LABA combination products, e.g., umeclidinium/vilanterol/fluticasone furoate.	Subjects on a LABA or ICS/LABA product do not need to be washed out provided they have been on a stable dose for at least 30 days prior to the Ipratropium Reversibility test at screening and this is continued through to end of V6. The steroid component should be $\leq$ 1000 mcg/day fluticasone propionate or equivalent. Subjects should abstain from LABA use prior to performing the Ipratropium Reversibility test, however (i.e., 24 hours for QD LABAs and 12 hours for BID LABAs). Subjects on a LAMA/LABA combination need to be switched to the LABA only product at least 7 days prior to the Ipratropium Reversibility test at screening and maintained during the course of the study through to end of V6. Subjects on a LAMA/ICS/LABA combination need to be switched to the ICS/LABA product at least 7 days prior to the Ipratropium Reversibility test at screening and maintained during the course of the study through to end of V6.
Oral theophyllines e.g., theophylline, aminophylline.	12 hours prior to the Ipratropium Reversibility test at screening. Theophyllines must be withheld at least 12 hours prior to any spirometry and during the entire visit when serial spirometry is being performed.

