## 4.11.1 Extent of Exposure

Descriptive summaries (mean, SD, median, min, max) will be presented for the number of vials taken and the study drug exposure by treatment group (Safety Set).

Study drug exposure will be calculated as the number of days from first to last dose date of study drug for the treatment period.

Study drug exposure (Days) = Date of last dose – Date of first dose + 1

For subjects who early withdraw, and for whom the last dose date from the End of Treatment eCRF page is unknown, the date of last available in-clinic dosing, date of withdrawal, and/or dosing recorded via the diary will be used, whichever is later.

All data for study drug exposure will be listed.

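### The SAP's whole-period compliance figure can miss a run of skipped doses just before the Day 85 trough; the per-protocol criterion should also cover the last visit interval

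*SAP*

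**What the plan says.** **Protocol 5.1.2** has compliance checked at Visits 4 to 6. A compliant subject is one who has "received 80% - 120% of the total number of doses that should have been administered in between study visits". The main source is the count of used and unused vials, with diary entries as the fallback where vials are missing. The stated consequence is: "Subjects who are non-compliant will be re-trained on the requirements of the study".

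**SAP 4.9** defines a single percentage per subject, "Number of vials taken / Number of expected vials" times 100. Expected vials are one per day of exposure, and SAP 4.11.1 gives exposure as "Date of last dose – Date of first dose + 1". The limits are inclusive: "If the compliance is outside of 80%-120%, a subject is considered non-compliant". There is no calculation by visit interval.

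**SAP 4.4.2** includes "Subjects who are not 80-120% compliant with study medication" in an open list of possible major deviations and names no period, so the SAP 4.9 definition is the only one available. None of the other five listed items concerns missed doses. Decisions on PP exclusion are taken at the blinded data review, before unblinding. SAP 4.5 restricts the PP set to the primary endpoint, and Table 6 labels that analysis supportive.

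**Protocol 6.2.4** places the clinic dose at Visit 6 after the two pre-dose spirometry sessions that form the trough.

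**The concern.** The primary endpoint is a trough for a once-daily drug, so the doses taken in the days before Visit 6 bear most directly on whether the Day 85 value reflects treatment. A subject who stops at home for the last weeks but attends Visit 6 is dosed there after the trough has been recorded. The last dose date then becomes the Visit 6 date, and the gap is averaged over the whole treatment period. The rule limiting the primary analysis to data before treatment discontinuation does not help, because by dates this subject has not discontinued.

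The PP set is meant to leave out subjects whose violations bear significantly on the primary endpoint. A compliance criterion that cannot see a gap immediately before that endpoint serves the purpose poorly. The same subject would also be non-compliant at the Visit 6 site check and compliant in the SAP's table.

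For scale, Table 5-1 sets the washout for other long-acting muscarinic antagonists at "7 days prior to the Ipratropium Reversibility test at screening and prohibited during the course of the study through to end of V6"; a 17-day gap is 17/7 = 2.4 times those 7 days. This is an analogy within the documents, not evidence on how fast revefenacin's effect wears off.

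**Working it through.** The documents contain no worked compliance figure to reproduce, so the check applies the SAP's formula to a defined case.

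**Inputs**
- Compliance = 100 × vials taken / expected vials; 80% and 120% both count as compliant (SAP 4.9).
- Expected vials = last dose date − first dose date + 1 (SAP 4.9 and 4.11.1).
- Visit 5 nominal Day 57; Visit 6 nominal Day 85, window Days 78 to 92 (Protocol Table 1-1).
- Clinic dose at Visit 6, after the trough (Protocol 6.2.4).
- Assumption: no other dose is missed.

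**Step 1: SAP figure, Visit 6 on Day 85.** The subject doses on Days 1 to 67, misses Days 68 to 84, and is dosed in clinic on Day 85.
- Expected: 85 − 1 + 1 = 85. Missed: 84 − 68 + 1 = 17. Taken: 85 − 17 = 68.
- 68/85 = 80.0%: compliant.
- One more missed dose: 67/85 = 78.8%, non-compliant. So 17 is the maximum.

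**Step 2: protocol figure for the last interval.** Doses due from Visit 5 to the day before Visit 6 are Days 57 to 84, which is 28. Days 57 to 67 were taken, which is 11.
- 11/28 = 39.3%: non-compliant. Counting home doses only, 10/27 = 37.0%.
- This rule tolerates 5 missed doses (23/28 = 82.1%) but not 6 (22/28 = 78.6%).

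**Step 3: across the Visit 6 window, Visit 5 on Day 57**

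| Visit 6 | Longest gap that passes | Overall | One more missed | Last interval |
|---|---|---|---|---|
| Day 78 | 15 days | 63/78 = 80.8% | 62/78 = 79.5% | 6/21 = 28.6% |
| Day 85 | 17 days | 68/85 = 80.0% | 67/85 = 78.8% | 11/28 = 39.3% |
| Day 92 | 18 days | 74/92 = 80.4% | 73/92 = 79.3% | 17/35 = 48.6% |

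**Step 4: possible effect on the PP estimate.** The documents do not say how often such gaps occur. Assume a share p of revefenacin subjects in the PP set has one, and that each has lost the whole drug effect at Day 85. With the design effect of 100 mL, the PP difference falls by about p × 100 mL: 1 mL at p = 1%, 5 mL at 5%, 10 mL at 10%. The design standard deviation of 245 mL with 128 per arm gives a standard error of 245 × √(2/128) = 30.6 mL. These shifts are therefore about 0.03, 0.16 and 0.33 standard errors. The values of p are illustrative.

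**The case against.** **The PP set is not fixed by the listed criterion.** A reader might infer that the Step 1 subject stays in the PP set. The documents do not say so. The deviation list in SAP 4.4.2 is open, SAP 4.5 defines the set by impact on the primary endpoint, and the blinded review could exclude this subject. This stands. What remains is that no written rule does so, and the decision is left to case-by-case judgement.

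**No protocol PP rule is broken.** A reader might also infer that the SAP overrides a protocol criterion. Protocol 5.1.2 is a site check that leads to re-training. Protocol 7.2.3 and 8.4 set no compliance threshold for the PP set, and Protocol section 7 allows the SAP to modify the planned analyses. This also stands. The point is an unreconciled definition: the same limits are used over a different period, and only the SAP attaches an analysis consequence.

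**The 17-day case is a boundary.** It needs an otherwise perfect record and lands exactly on 80.0%. That is true of 17, but shorter gaps pass more easily. With Visit 6 on Day 85, any 6 to 17 missed doses confined to the last interval fail the interval rule and pass the overall one (6 missed: 79/85 = 92.9%).

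**The consequence is small.** The PP analysis is supportive, and dilution toward zero works against the drug in a superiority trial. This stands.

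**Interval counts may be unavailable in a public health emergency.** Under Protocol 6.6, visits may be held by telephone and vials returned later. Protocol 5.1.2 already provides the diary as fallback, so this is manageable.

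**Conclusion.** The concern holds in a limited form. As written, the SAP's compliance criterion does not remove a subject with up to 17 consecutive missed doses just before a Day 85 Visit 6, or 15 to 18 across the visit window, although compliance in the last interval is 39% in the Day 85 case. This assumes no other missed dose and a clinic dose at Visit 6. Blinded review may still exclude the subject.

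The effect is confined to the supportive PP analysis. Its direction is toward zero, and its size is unknown because neither the frequency of such gaps nor the loss of effect during them is given. A reader might infer that the primary result is at risk. It is not: the FAS analysis does not use the compliance criterion, and the sample size is unaffected. The change is worth making because it is cheap and makes the PP set better reflect troughs measured on drug.

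**What to change.** - **SAP 4.9:** keep the overall figure and add compliance for each visit interval, as in Protocol 5.1.2, using actual visit dates. Use vial counts, with diary entries where vials are missing, including after telephone visits. State whether clinic doses count (28 or 27 doses due in the nominal last interval).
- **SAP 4.4.2:** state that the 80-120% PP criterion applies to the interval ending at Visit 6 as well as overall.

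The cost is SAP wording and some programming on vial counts and diary compliance data that the protocol already has recorded, plus a slightly smaller PP set. No visit, procedure or FAS analysis changes. The wording should be settled before unblinding.

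A further rule that drops Day 85 troughs with no diary dose on the previous day is not recommended. It would exclude a value for one missed or unrecorded dose, which is far stricter than 80-120%. It would also make the fallback source the primary one, and it needs daily dose dates that the documents do not show to be in the database.
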